5.2.1. Primary endpoint

Reduction of dose volume of rectum receiving x Gy as specified below, which is measured from CT simulation scans acquired pre and post SpaceOAR hydrogel injection(i.e.Vx Gy):

- For conventionally fractionated regimen: V70Gy
- For moderately hypofractionated regimen: V46Gy, V37Gy
- For ultrahypofractionated regimen: V29 Gy, V18. 1 Gy, V36 Gy

Dose to the anterior rectum is quantified by computing a rectal dose-volume histogram (DVH).

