5.2.2. Second endpoints

1. EPIC bowel and urinary Assessment composite score at 2 weeks, 6 weeks and 3 months post radiotherapy

2. EPIC Sexual Assessment composite score at 2 weeks, 6 weeks, and 3 months post radiotherapy
3. Quality of Life at 2 weeks, 6 weeks and 3 months post radiotherapy (QOL)
4. Whether there is SpaceOAR hydrogel between the posterior prostatic capsule and the anterior rectal wall at 6 weeks post radiotherapy.
5. Whether the SpaceOAR hydrogel between the prostate and the anterior rectal wall is absorbed in 10 months post radiotherapy.
6. Rectal adverse event (CTCAE)
7. AEs/SAEs related to SpaceOAR hydrogel

6. Study Design

The SpaceOAR real world study is a retrospective and prospective, single arm study, and this study protocol is for the second part of the SpaceOAR real world study in which long term follow-up will be performed (up to 1 year) outside Boao Medical Tourism Pilot Zone. Subjects with localized T1-T2 prostate cancer who have already been injected with the SpaceOAR and have received radiotherapy or will receive radiotherapy will be enrolled, and clinical data related to radiotherapy will be collected.

For subjects who have already completed radiotherapy before study kick-off, clinical data will be collected retrospectively, such as data related to radiotherapy, AE (if any) and MRI (if any), and follow up will be performed, if applicable.

For subjects who receive therapy after study kick-off, radiotherapy relevant clinical data will be collected, and follow up visits after radiotherapy will be scheduled to assess urinary, bowel, sexual functions and AE.

All administration of SpaceOAR hydrogel will be completed by trained urologists in the hospital in Boao.

All radiotherapy planning will be made according to clinical practice and stage of Pca at discretion of the doctors.

[figure not shown]

Figure 6-1 Space OAR observational Study Design

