A subject will be considered lost to follow-up if he fails to complete 30 days follow-up visits and is unable to be contacted by the study site staff after at least three documented attempts, at which point an End of Study form should be completed. Before a participant is deemed lost to follow up, the investigator or designee will make every effort to regain contact with the participant (where possible, 3 telephone calls and, if necessary, a certified letter to the participant's last known mailing address or local equivalent methods). These contact attempts should be documented in the participant's medical record or study file. (only for patients enrolled prospectively).

8.4. *End-of-Study Definition*

A subject is considered to have completed the study if he has completed all phases of study including the last visit or last scheduled procedure shown in the data collection schedule.

A clinical trial is considered completed when participants are no longer being examined or the last participant's last study visit has occurred.

9. Study Methods

9.1. *Data Collection*

The data collection schedule is shown in Table 9-1.

Table 9-1: Data Collection Schedule

Procedure/Assessment	Before RT	RT	After RT			
			2W (\pm 3days)	6W (\pm 7days)	3M (\pm 15days)	10M (\pm 30 days)
Informed consent	X					
PSA	X			X		X
CT	X*					
MRI	X*			X		X
Radiotherapy		X				
EPIC questionnaire	X		X	X	X	
EQ-5D-5L questionnaire	X		X	X	X	
Concomitant medication	X	X	X	X	X	X
Adverse event	X	X	X	X	X	X
Protocol Deviation	X	X	X	X	X	X
Device Deficiency[#]	X	X	X	X	X	X

NOTE:1. Data at baseline such as demography, medical history, Pca, etc. refer to SpaceOAR RWS (U0720).
 2.*CT&MRI for mapping, which used to make RT planning, 2 times.
 3.# DD of Space OAR hydrogel.

9.2. *Study Candidate Screening*

Patients diagnosed with localized prostate cancer who have been injected with SpaceOAR hydrogel in SpaceOAR RWS in Hainan (U0720) will be invited to participate in this study.

9.3. *Informed Consent*

For patients who receive radiotherapy after SpaceOAR injected, investigator will introduce study information to subject and get ICF. Once the ICF is signed, he is enrolled in study. If he fails to receive radiotherapy after ICF signed, the subjects are screening failure.

9.4. *study visits*

The subject of SpaceOAR RWS are going to participate in this study when he completed last visit. the process of SpaceOAR RWS is summarized below.

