- Patients who diagnosed with T1-T2 prostate cancer and scheduled to receive RT will be screened and recommended to participate in SpaceOAR RWS in Hainan. After informed consent is done fully, Mapping CT and MRI will be conducted. (Shanxi Provincial Cancer Hospital is preferred.)
- Subjects go to Boao Yiling Life Care Center in Hainan to receive SpaceOAR gel injection voluntarily, which is completed by trained and qualified urologist.
- After discharge, subjects will receive Mapping CT and MRI to make RT plan, then receive RT. (Shanxi Provincial Cancer Hospital is preferred, i.e., enrolled in this study)
- At 30 days after SpaceOAR injection, a phone visit will be completed. Then subject complete all visits.

Subjects who have been injected with SpaceOAR in Hainan BOAO return to participate in this observational study. subjects receive radiotherapy per site's clinical practice, then will be followed in 2 weeks, 6 weeks, 3 months and 10 month after RT.

1) Before RT

RT planning before and after SpaceOAR hydrogel injection will be made (such as planning type of EBRT, planning RT regimen, CTV, PTV and constraint of risk organs, etc.). The RT planning of the subjects will be determined by the investigators based on the current clinical practice and PCa staging and conditions of the subjects.

The questionaries of EPIC and EQ-5D-5L will be completed, adverse event and Device Deficiency (if applicable) will be assessed and collected.

Note: The subject's demographic, medical history, genitourinary history, prostate treatment, PCa therapies, PCa staging, Gleason score, etc., are collected in the SpaceOAR RWS(U0720).

2) RT

RT is conducted according to RT planning after SpaceOAR injection; adverse event and Device Deficiency will be collected, if applicable.

3) Follow-ups after RT

2 weeks post RT: the questionaries of EPIC and EQ-5D-5L will be completed to assess the functions of urinary, rectum and health related Quality of life; Adverse event and Device Deficiency will be collected, if applicable.

6 weeks post RT: the questionaries of EPIC and EQ-5D-5L will be completed to assess the functions of urinary, rectum and health related Quality of life; Adverse event and Device Deficiency will be collected, if applicable; MRI will be performed.

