## **1.6 Follow-up schedule**

Subjects who have been injected with SpaceOAR in Hainan BOAO, will receive radiotherapy per site's clinical practice, then will be followed in 2 weeks, 6 weeks, 3 months and 10 months after RT.

- Before RT

RT planning before and after SpaceOAR hydrogel injection will be made (such as planning type of EBRT, planning RT regimen, CTV, PTV and constraint of risk organs, etc.). The RT planning of the subjects will be determined by the investigators based on the current clinical practice and PCa staging and conditions of the subjects.

The questionaries of EPIC and EQ-5D-5L will be completed, adverse event and Device Deficiency (if applicable) will be assessed and collected.

Note: The subject's demographic, medical history, genitourinary history, prostate treatment, PCa therapies, PCa staging, Gleason score, etc., are collected in the SpaceOAR RWS(U0720).

- RT

Radiotherapy will be conducted per planning RT; adverse event and Device Deficiency will be collected, if applicable.

- Follow-ups after RT

2 weeks post RT: the questionaries of EPIC and EQ-5D-5L will be completed to assess the functions of urinary, rectum and health related Quality of life; Adverse event and Device Deficiency will be collected, if applicable.

6 weeks post RT: the questionaries of EPIC and EQ-5D-5L will be completed to assess the functions of urinary, rectum and health related Quality of life; Adverse event and Device Deficiency will be collected, if applicable; MRI will be performed.

3 months post RT: the questionaries of EPIC and EQ-5D-5L will be completed to assess the functions of urinary, rectum and health related Quality of life; Adverse event and Device Deficiency will be collected, if applicable.

10 months post RT: MRI will be performed; Adverse event and Device Deficiency will be collected, if applicable.

NOTE: For subjects who have received RT (after SpaceOAR injection), applicable follow up will be performed after participation in this study to assess adverse event and device deficiency, if any, then to collect clinical data. The clinical data before participation will be collected retrospectively at same time.

The data collection schedule is shown in below table:

Procedure/Assessment	Before RT	RT	After RT			
			2W ( $\pm$ 3days)	6W ( $\pm$ 7days)	3M ( $\pm$ 15days)	10M ( $\pm$ 30 days)
Informed consent	X					
PSA	X			X		X
CT	X*					
MRI	X*			X		X
Radiotherapy		X				

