### **3 ENDPOINT ANALYSIS**

#### **3.1 Primary Endpoints**

Reduction of dose volume of rectum receiving x Gy as specified below, which is measured from CT simulation scans acquired pre and post SpaceOAR hydrogel injection, (i.e. Vx Gy):

- For conventionally fractionated regimen: V70Gy
- For moderately hypofractionated regimen: V46Gy, V37Gy
- For ultrahypofractionated regimen: V29 Gy, V18. 1 Gy, V36 Gy

Dose to the anterior rectum is quantified by computing a rectal dose-volume histogram (DVH).

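### Does the primary endpoint need a rule that a subject's pre- and post-injection radiotherapy plans share planning parameters?

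*Protocol*

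**What the plan says.** The endpoint (Protocol 5.2.1, repeated in SAP 3.1) is the reduction in rectal Vx, "measured from CT simulation scans acquired pre and post SpaceOAR hydrogel injection". The dose level x depends on the regimen, for example "For moderately hypofractionated regimen: V46Gy, V37Gy". Table 9-1, note 2, schedules the scans that this needs: "CT&MRI for mapping, which used to make RT planning, 2 times".

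On how the plans are made:

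- Protocol 6: "All radiotherapy planning will be made according to clinical practice and stage of Pca at discretion of the doctors".
- Protocol 9.4 and SAP 1.6, before RT: "RT planning before and after SpaceOAR hydrogel injection will be made (such as planning type of EBRT, planning RT regimen, CTV, PTV" and the constraints for organs at risk.
- Protocol 9.4 then adds that "RT planning of the subjects will be determined by the investigators based on the current clinical practice and PCa staging and conditions of the subjects".
- Protocol 9.4, RT: "RT is conducted according to RT planning after SpaceOAR injection".
- Protocol 9.4, in its summary of U0720, on the pre-injection scan: "Mapping CT and MRI will be conducted. (Shanxi Provincial Cancer Hospital is preferred".

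On bias, Protocol 6.4 relies on Vx being objective and derived from a dose-volume histogram (DVH) computed in one hospital. Protocol 10.2.2 and SAP 4.2 rely on the DVH alone. Neither document says that a subject's two plans share planning parameters.

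**The concern.** A CT scan has no Vx of its own. The value comes from the anatomy on the scan and from the plan built on it. If a subject's two plans differ in technique, margins, contours or constraints, the change in Vx mixes that difference with the displacement of the rectum by the hydrogel.

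The listed bias controls do not address this. A DVH reads objectively whatever plan it is given, so computing it in one place governs the reading and not the building of the plan. The pre-injection plan is also never delivered. It serves as the reference for the study's only contrast with and without hydrogel, and the text does not say how it must be constructed.

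What would be at stake is attribution. Protocol 4.2 wants the data to speak to the device's performance. SAP 2 allows the analyses to go into regulatory submissions. SAP 3.1.3 lists a paired t-test or Wilcoxon signed-rank test for before/after assessments, although no hypothesis is stated. Planning differences could inflate the reported reduction or hide part of it.

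**Working it through.** The documents state no figure that depends on this point, so there is nothing to reproduce. The check sets the text beside each ingredient of a plan.

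**1. What the text implies for each ingredient**

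| Ingredient | Source | Common to a subject's two plans? |
|---|---|---|
| Regimen | Protocol 5.2.1, thresholds by regimen | Implied. With plans under two regimens there would be no single set of thresholds for computing a reduction. |
| Type of external-beam treatment | Protocol 9.4, SAP 1.6 | Not stated. Set by clinical practice. |
| Target volumes (CTV, PTV) | Same | Not stated. Driven by stage and condition, which belong to the patient. |
| Organ constraints | Same | Not stated. Set by clinical practice. |
| DVH computation | Protocol 6.4 | Same hospital. |

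Protocol 9.4 and SAP 1.6 cover planning before and after injection in one sentence, with one list of contents, under one visit. The stated drivers are clinical practice, the stage of the cancer and the condition of the subject. Nothing suggests that practice or stage changes between the two scans. Protocol 7.2 places the radiotherapy at this site.

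**2. The hospital that is only preferred**

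That wording concerns where the mapping scan is taken in the parent study. It does not say that the comparison plan is built elsewhere, and Protocol 6.4 puts the DVH computation in one hospital. Where the scan is taken says little about whether plan parameters match.

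**3. Size**

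If k of n pairs differ in planning by an average of D, the mean change moves by (k/n) × D.

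- n = 20, k = 1: 1/20 = 5.0% of D.
- n = 14, k = 1: 1/14 = 7.1% of D.
- k = n: the full D, at any n.

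These are properties of any mean. The documents give no Vx values, no SD and no planning variability, so k and D are unknown and the sign of D is open. The arithmetic gives no estimate of bias for this study.

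**4. What a matching rule would require**

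- *A pre-injection planning scan for every subject.* Some subjects completed radiotherapy before study start (Protocol 6). U0720 also takes in patients injected before its own start (Protocol 7.1). Protocol 13 does not count missing tests in retrospective data as deviations. The scan cannot be assumed to exist in every case.
- *New planning work.* Protocol 16.2 describes a study that uses data generated in clinical practice. Re-planning old scans to match later delivered plans goes beyond that.
- *Timing.* Protocol Version B is dated January 2022, the planned duration is about 15 months, and the SAP is dated April 2024. The start date is not given, but many of the plans may already have been made.
- *A choice of question.* Plans with identical objectives isolate the geometric effect of the spacer. Plans as practice would make them on each anatomy include any change that planners make because the spacer created room, and such a change is a consequence of the device. The real-world aim in Protocol 4.2 makes the second question legitimate.

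**The case for a change.** The strongest case for a change runs as follows. The omission is certain, because no section of either document fixes technique, margins, contours or constraints within a subject. A shared regimen, even if implied, does not cover those items. Random differences may partly average out, but a difference common to all pairs does not shrink with n. A descriptive label does not make a contrast interpretable, and the results may reach a regulator. A sentence of clarification and a few recorded parameters would cost little, and the delivered treatment would be untouched.

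Much of this stands as fact. The documents are silent, DVH computation does not make two plans comparable, and a systematic difference would carry straight into the mean. What does not follow is that the plan needs altering. The argument shows what could happen if plans diverged, but no passage indicates that they do. The silence is also that of two documents only: the pre-injection mapping belongs to U0720, and the SAP is written against eCRF version 5.0. Either may already fix or record the plan parameters. The stronger remedy, re-planning with common objectives, rests on scans that may not exist and replaces a real-world comparison with a different one. The weaker remedy, saying whether the two plans used common parameters and showing them where recorded, is ordinary reporting that a competent analyst and medical physicist would supply when presenting Vx.

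**Conclusion.** No change to the plan follows. This is missing detail that the site and the analysts would ordinarily fill sensibly: one patient, one implied regimen, and one parameter list governed by clinical practice. The primary summary is descriptive, with no hypothesis, no sample-size calculation and at most 20 subjects, so no error rate or decision rule depends on the point.

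The size of any planning contribution to the Vx change is unknown in both amount and direction.

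The conclusion rests on two assumptions. First, the site plans both scans under its usual practice with the same regimen. Second, nothing in U0720 or the eCRF, neither of which was available, directs otherwise. If plans proved to differ systematically for reasons unrelated to the hydrogel, the reported change could not be credited to the hydrogel alone. That would be a matter for interpreting the result.

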9.5. Study Completion

When last subject complete follow up visit at 10 months post RT and data collection is complete, this study will come to an end.

9.6. Source Documents

It is preferable that original source documents are maintained, when available. In lieu of original source documents, certified copies are required to be maintained. A certified copy is a copy (irrespective of the type of media used) of the original record that has been verified (i.e., by a dated signature or by generation through a validated process) to have the same information, including data that describe the context, content, and structure, as the original.

10. Statistical Considerations

10.1. Study hypotheses

There are no hypotheses for this second stage of SpaceOAR Real World study. All the endpoints are descriptive in nature. The endpoints in the study include the following:

Primary endpoint

Reduction of dose volume of rectum receiving x Gy as specified below, which is measured from CT simulation scans acquired pre and post SpaceOAR hydrogel injection, (i.e. V_x Gy):

- For conventionally fractionated regimen: V70Gy
- For moderately hypofractionated regimen: V46Gy, V37Gy
- For ultrahypofractionated regimen: V29 Gy, V18. 1 Gy, V36 Gy

Dose to the anterior rectum is quantified by computing a rectal dose-volume histogram (DVH).

Secondary endpoints

1. EPIC bowel and urinary assessment composite score at 2 weeks, 6 weeks, and 3 months post radiotherapy
2. EPIC sexual assessment composite score at 2 weeks, 6 weeks, and 3 months post radiotherapy
3. Quality of Life at 2 weeks, 6 weeks, and 3 months post radiotherapy (QOL)
4. Whether there is SpaceOAR hydrogel between the posterior prostatic capsule and the anterior rectal wall at 6 weeks post radiotherapy.
5. Whether the SpaceOAR hydrogel between the prostate and the anterior rectal wall is absorbed in 10 months post radiotherapy.
6. Rectal adverse event (CTCAE)
7. AEs/SAEs related to SpaceOAR hydrogel

10.2. General Statistical Methods

10.2.1. Analysis Sets

The effectiveness set, and safety set include all subjects who have radiotherapy after injection of SpaceOAR hydrogel.

10.2.2. Control of Systematic Error/Bias

All patients who receive RT at the BOAO site after injection of SpaceOAR will be invited to enroll at a given time, to minimize selection bias. The primary endpoint is an objective measure, which is computed via DVH to reduce assessment bias.

10.2.3. The method of handling missing, incorrect data (including subjects' withdrawal and lost to follow-up) and unreasonable data

Missing data will not be imputed for primary analysis. Incorrect and unreasonable data will be clarified before database lock. Imputation with mean or median may be performed where applicable for the primary endpoint as a sensitivity analysis.

10.3. Data Analyses

Descriptive statistics will be used to summarize the study endpoints, such dose volume of rectum receiving x Gy, EPIC composite score, AEs. Continuous variables will be tabulated with mean, median, standard deviation, minimum, maximum. Categorical variables will be tabulated with frequencies, percentages along with the 95% confidence intervals when appropriate.

Any statistical analysis changes for the study endpoints will be described in the statistical analysis plan before the data analysis.

11. Data Management

11.1. *Data Collection, Processing, and Review*

Subject data will be recorded in a limited access secure electronic data capture (EDC) system.

The clinical database will reside on a production server hosted by Medidata EDC System. All changes made to the clinical data will be captured in an electronic audit trail and available for review by the sponsor or its representative. The associated Rave software and database have been designed to meet regulatory compliance for deployment as part of a validated system compliant with laws and regulations applicable to the conduct of clinical studies pertaining to the use of electronic records and signatures. Database backups are performed regularly.

The Investigator provides his/her electronic signature on the appropriate electronic case report forms (eCRFs) in compliance with local regulations. A written signature on printouts of the eCRFs must also be provided if required by local regulation. Changes to data previously submitted to the sponsor require a new electronic signature by the Investigator acknowledging and approving the changes.

Visual and/or electronic data review will be performed to identify possible data discrepancies. Manual and/or automatic queries will be created in the Medidata EDC system and will be issued to the site for appropriate response. Site staff will be responsible for resolving all queries in the database.

All access to the clinical database will be changed to “Read only” after all data is either “Hard Locked” or “Entry Locked”. Once acceptance of the final report or finalization of publications (as applicable) is received, final database storage and archiving activities may begin. Once all of the closeout activities are completed a request to IT is submitted to have the “Database Locked” or Decommissioned and all database access revoked.

11.2. *Data Retention*

The Principal Investigator or his/her designee or Investigational site will maintain all essential study documents and source documentation that support the data collected on the study subjects in compliance with applicable regulatory requirements. Documents must be retained for 10 years after the formal discontinuation of the clinical investigation of the product or retained for a long time in accordance with site’s requirements. These documents will be retained by BSC until the product/device is no longer in use in compliance with local regulations.

The Principal Investigator or his/her designee will take measures to prevent accidental or premature destruction of these documents. If for any reason the Principal Investigator or his/her designee withdraws responsibility for maintaining these essential documents, custody must be transferred to an individual who will assume responsibility and BSC must receive written notification of this custodial change. Sites are required to inform Boston Scientific in writing where paper or electronic files are maintained in case files are stored off site and are not readily available.

12. Amendment

The investigator should adhere to clinical trial protocol approved by EC. Any Amendment to the protocol (management information or study process modification, etc.) should be completed and reviewed by the sponsor during the study, then should be submitted to the EC for approval via the investigator. Only the amendment of protocol is approved by EC, the amended protocol should be implemented.

13. Deviations

An Investigator must not make any changes or deviate from this protocol, except to protect the life and physical well-being of a subject in an emergency. An investigator shall notify the sponsor and the reviewing IRB/EC, and the regulatory authority if applicable of any deviation from the investigational plan to protect the life or physical well-being of a subject in an emergency, and those deviations which affect the scientific integrity of the clinical investigation. Such notice shall be given as soon as possible, but no later than 5 working days after the emergency occurred, or per prevailing local requirements, if sooner than 5 working days.

All deviations from the investigational plan, with the reason for the deviation and the date of occurrence, must be documented and reported to the sponsor using EDC. Sites may also be required to report deviations to the IRB/EC, and the regulatory authority, per local guidelines and national/government regulations.

Deviations will be reviewed and evaluated on an ongoing basis and, as necessary, appropriate corrective and preventive actions (including but not limited to IRB/EC, regulatory authority notification, site re-training, or site discontinuation/termination) will be put into place by the sponsor.

Since this study is a prospective and retrospective, real world study without intervention based on standard medical care, missing data and tests are not deemed as study deviations for the retrospectively collected data. For prospectively collected data, deviations should be recorded, including but not limited to informed consent, inclusion criteria, follow-up visit etc.

14. Compliance

14.1. *Statement of Compliance*

This clinical investigation is financed by the study sponsor. Before the investigational site can be “Authorized to Enroll,” the investigational site must enter into a Clinical Study Agreement with the sponsor that details the financing of the study as well as the rights and obligations of the investigational site and the investigator. This study will be conducted in accordance with ISO 14155, ICH-GCP, ethical principles that have their origins in the Declaration of Helsinki, and applicable individual country laws and regulations. The study shall not begin until the required approval/favorable opinion from the IRB/EC and/or regulatory authority has been obtained, if appropriate. Also, the study shall not begin prior to issuance of the site Authorization to Enroll, as provided by the sponsor. Any additional

requirements imposed by the IRB/EC or regulatory authority shall be followed, if appropriate.

14.2. *Investigator Responsibilities*

The Principal Investigator of an investigational site is responsible for ensuring that the study is conducted in accordance with the Clinical Study Agreement, the clinical investigation plan/, the spirit of ISO 14155, ethical principles that have their origins in the Declaration of Helsinki, any conditions of approval imposed by the reviewing IRB/EC, and prevailing local and/or country laws and/or regulations, whichever affords the greater protection to the subject.

The Principal Investigator's responsibilities include, but are not limited to, the following.

- Prior to beginning the study, sign the Clinical Study Agreement and comply with the Investigator responsibilities as described in such Agreement.
- Provide his/her qualifications and experience to assume responsibility for the proper conduct of the study and that of key members of the site team through up-to-date curriculum vitae or other relevant documentation and disclose potential conflicts of interest, including financial, that may interfere with the conduct of the clinical study or interpretation of results.
- Make no changes in or deviate from this protocol, except to protect the life and physical well-being of a subject in an emergency; document and explain any deviation from the approved protocol that occurred during the clinical investigation.
- Create and maintain source documents throughout the clinical study and ensure their availability with direct access during monitoring visits or audits; ensure that all clinical-investigation-related records are retained per requirements.
- Ensure the accuracy, completeness, legibility, and timeliness of the data reported to the sponsor in the CRFs and in all required reports.
- Record, report, and assess (seriousness and relationship to the device/procedure) every adverse event as applicable per the protocol and observed device deficiency. For prospective cohort, investigator will analyze cause of adverse events and write an analysis report with sponsor, then provide suggestion such as continuation, suspension, or termination of study according to China GCP. All will be reviewed by EC.
- Report to sponsor, per the protocol requirements, all reportable events.
- Report to the IRB/EC and regulatory authorities any SAEs and device deficiencies that could have led to a SADE and potential/USADE or UADE, if required by applicable laws or regulations or this protocol or by the IRB/EC, and supply BSC with any additional requested information related to the safety reporting of a particular event.
- Allow the sponsor to perform monitoring and auditing activities, and be accessible to the clinical research monitor or auditor and respond to questions during monitoring visits or audit(s).

- Allow and support regulatory authorities and the IRB/EC when performing auditing activities.
- Ensure that informed consent is obtained in accordance with applicable laws, this protocol and local IRB/EC requirements.
- Provide adequate medical care to a subject during and after a subject's participation in a clinical study in the case of adverse events, as described in the Informed Consent Form (ICF).
- Inform the subject of the nature and possible cause of any adverse events experienced.
- Inform the subject of any new significant findings occurring during the clinical investigation, including the need for additional medical care that may be required.
- Provide the subject with well-defined procedures for possible emergency situations related to the clinical study, and make the necessary arrangements for emergency treatment, including decoding procedures for blinded/masked clinical investigations, as needed.
- Ensure that clinical medical records are clearly marked to indicate that the subject is enrolled in this clinical study.
- Ensure that, if appropriate, subjects enrolled in the clinical investigation are provided with some means of showing their participation in the clinical investigation, together with identification and compliance information for concomitant treatment measures (contact address and telephone numbers shall be provided).
- Inform, with the subject's approval or when required by national regulations, the subject's personal physician about the subject's participation in the clinical investigation.
- Make all reasonable efforts to ascertain the reason(s) for a subject's premature withdrawal from clinical investigation while fully respecting the subject's rights.
- Ensure that an adequate investigation site team and facilities exist and are maintained and documented during the clinical investigation.

All investigators will provide their qualifications and experience to assume responsibility for their delegated tasks through up-to-date curriculum vitae or other relevant documentation and disclose potential conflicts of interest, including financial, that may interfere with the conduct of the clinical study or interpretation of results.

